### 6.3.3 Treatment interruption and treatment discontinuation

If the administration of INC280 is temporarily interrupted for reasons other than toxicity, then treatment with INC280 may be resumed at the same dose. If the treatment with INC280 is withheld due to toxicity, the dose modification guidelines in [Table 6-3](#) should be followed. In any case, scheduled visits and all assessments (including tumor assessments) should continue to be performed, as described in [Table 7-1](#).

If the treatment with INC280 is withheld for more than 21 consecutive days (counting from the first day when a dose was interrupted), then INC280 should be permanently discontinued. Under exceptional circumstance, when the investigator believes that continuing treatment may still derive clinical benefit for the patient, study treatment may be resumed. However, the investigator must discuss and receive approval from Novartis Medical Lead or designee prior to continuing INC280 treatment.

Patients who discontinue the study due to a study drug related AE or an abnormal laboratory value must be followed as described in [Section 6.3.4](#).

### 6.3.4 Follow-up for toxicities

All patients will be followed for safety until 30 days after the last dose of INC280. Patients whose treatment is temporarily interrupted or permanently discontinued due to an AE or abnormal laboratory value must be followed until resolution or stabilization of the event, whichever comes first, including all study assessments appropriate to monitor the event.

An unscheduled assessment should be performed in all cases below where toxicity monitoring is recommended more frequently than defined by the schedule of assessments. Subsequent monitoring must be performed as per the regular visit schedule.

All patients should receive best supportive care (BSC) as per standard local practice for the treatment of pre-existing medical conditions or adverse events that may arise during the study. BSC is defined as drug or non-drug therapies, nutritional support, physical therapy, or any other treatment alternative that the investigator believes to be in the patient's best interest, but excluding other anti-neoplastic treatments (with the exception of radiotherapy for control of bone metastases – see [Section 6.4.1](#)).

**Table 6-4 Follow-up evaluations for selected toxicities\***

TOXICITY	FOLLOW-UP EVALUATION
HEMATOLOGICAL Febrile neutropenia, Neutropenia $\geq$ CTCAE grade 3 Thrombocytopenia $\geq$ CTCAE grade 3 Anemia $\geq$ CTCAE grade 3	Test weekly (or more frequently if clinically indicated) until $\leq$ CTCAE grade 2. Perform physical exam for check on bruising in case of major thrombocytopenia.
RENAL Serum creatinine $\geq$ CTCAE grade 2	Test weekly (or more frequently if clinically indicated) until $\leq$ CTCAE grade 1 or baseline. Patients will be instructed to increase hydration until resolution to $\leq$ CTCAE grade 1 or baseline.

TOXICITY	FOLLOW-UP EVALUATION
HEPATIC  Isolated total bilirubin elevation	
Total bilirubin CTCAE Grade 1: Monitor LFTs per protocol or more frequently if clinically indicated
 
Total bilirubin CTCAE Grade 2: Weekly monitoring of LFTs, or more frequently if clinically indicated, until resolved to <math>\leq 1.5 \times</math> ULN
 
Total bilirubin CTCAE Grade 3: Weekly monitoring of LFTs, or more frequently if clinically indicated, until resolved to <math>\leq 1.5 \times</math> ULN. If resolved in <math>> 7</math> days, after discontinuing the patient from INC280 permanently, the patient should be monitored weekly (including LFTs), or more frequently if clinically indicated, until total bilirubin have resolved to baseline or stabilization over 4 weeks
 
Total bilirubin CTCAE Grade 4: After discontinuing the patient from INC280 permanently, the patient should be monitored weekly (including LFTs), or more frequently if clinically indicated, until total bilirubin have resolved to baseline or stabilization over 4 weeks

Isolated AST/ALT elevation	
AST/ALT CTCAE Grade 2 elevation: For patients with baseline value <math>\leq 3.0 \times</math> ULN: repeat LFTs as soon as possible, preferably within 48-72 hours from awareness of the abnormal results; if abnormal lab values are confirmed upon the repeat test, then monitor LFTs weekly, or more frequently if clinically indicated, until resolved to <math>\leq 3.0 \times</math> ULN For patients with baseline value <math>> 3.0 - 5.0 \times</math> ULN: monitor LFTs per protocol or more frequently if clinically indicated
 
AST/ALT CTCAE Grade 3 elevation: For AST/ALT elevation <math>> 5.0 - 10.0 \times</math> ULN:           
 
For patients with baseline value <math>\leq 3.0 \times</math> ULN: repeat LFTs as soon as possible, preferably within 48-72 hours from awareness of the abnormal results; monitor LFTs weekly, or more frequently if clinically indicated, until resolved to <math>\leq 3.0 \times</math> ULN
 
For patients with baseline value <math>> 3.0 - 5.0 \times</math> ULN: repeat LFTs as soon as possible, preferably within 48-72 hours from awareness of the abnormal results; if abnormal lab values are confirmed upon the repeat test, then monitor LFTs, weekly, or more frequently if clinically indicated, until resolved to <math>\leq 5.0 \times</math> ULN
 
 
 
For AST/ALT elevation <math>> 10.0 - 20.0 \times</math> ULN:           
 
Repeat LFTs as soon as possible, preferably within 48-72 hours from awareness of the abnormal results; monitor LFTs weekly, or more frequently if clinically indicated, until resolved to <math>\leq</math> baseline
 
 
 
AST/ALT CTCAE Grade 4 elevation: Repeat LFTs as soon as possible, preferably within 48-72 hours from awareness of the abnormal results; monitor LFTs weekly, or more frequently if clinically indicated, until resolved to baseline or stabilization over 4 weeks.

HEPATIC  Combined AST or ALT and total bilirubin elevation	
Combined elevations of AST or ALT and total bilirubin: After discontinuing the patient from INC280 permanently, repeat LFTs as soon as possible, preferably within 48 hours from awareness of the abnormal results, then with weekly monitoring of LFTs, or more frequently if clinically indicated, until AST, ALT, or bilirubin have resolved to baseline or stabilization over 4 weeks.
 
Core LFTs consist of ALT, AST, GGT, total bilirubin (fractionated [direct and indirect], if total bilirubin <math>> 2.0 \times</math> ULN), and alkaline phosphatase (fractionated [quantification of isoforms], if alkaline phosphatase <math>> 2.0 \times</math> ULN.)

TOXICITY	FOLLOW-UP EVALUATION
METABOLIC Asymptomatic amylase or lipase $\geq$ CTCAE grade 3	Test weekly (or more frequently) until $\leq$ CTCAE grade 2. A CT scan or equivalent imaging procedure to assess the pancreas, liver, and gallbladder is recommended within 7 days of the first occurrence of any $\geq$ CTCAE grade 3 result, to exclude disease progression or potential other liver or pancreatic disease.
CARDIAC $\geq$ CTCAE grade 3  QTcF $\geq$ 501 ms (CTCAE grade 3)	Test weekly (or more frequently) until $\leq$ CTCAE grade 2.  When QTcF $\geq$ 501 ms (CTCAE grade 3), perform the following: 

Call the study's central ECG review laboratory immediately and request an immediate manual read of the ECG.

Perform an analysis of serum potassium, calcium, phosphorus, and magnesium, and if below lower limit of normal, correct with supplements to within normal limits.

Review concomitant medication usage for the potential to inhibit CYP3A4/5 (Table 6-5) and/or to prolong the QT-interval (Table 6-6).

Check compliance with correct dose and administration of INC280.

 Perform a repeat ECG within one hour of the first QTcF of $\geq$ 501 ms. 

If QTcF remains <math>\geq</math> 501 ms, repeat ECG as clinically indicated, but at least once daily until the QTcF returns to <math><</math> 501 ms.

 Repeat ECGs 7 days and 14 days (and then every 21 days) after dose resumption for all patients who had therapy interrupted due to QTcF $\geq$ 501 ms. 

If QTcF of <math>\geq</math> 501 ms recurs, repeat ECGs as described above.

 Notes: 

The investigator should contact the Novartis Medical Lead or designee regarding any questions that arise if a patient with QTcF prolongation should be maintained on study.

If the central ECG report shows a QTcF <math>\geq</math> 501 msec (not previously documented on the site machine), contact the patient and instruct him/her to suspend INC280 and return for a repeat ECG as soon as possible. The central ECG reader should be called for a manual read of the repeat ECG immediately, and the above guidance followed.

TOXICITY	FOLLOW-UP EVALUATION
GASTROINTESTINAL	
Diarrhea	
Initiate anti-diarrhea treatment after first signs of abdominal cramping, loose stools or overt diarrhea.
 
Consider/Investigate potential concomitant medication, food or comorbidity driven causes of diarrhea (including infectious causes) and remedy these causes if possible (e.g. discontinuation of concomitant medication, dietary modification, treatment of comorbidity).
 
The patient should be monitored for signs of dehydration and instructed to take preventive measures against dehydration as soon as diarrhea occurs. Antidiarrheal medication must be initiated at the first sign of abdominal cramping, loose stools or overt diarrhea. Concomitant medication for the treatment of diarrhea should follow local practice and the investigator's best judgment and may follow "the recommended guidelines for the treatment of cancer treatment-induced diarrhea" (Benson et al 2004). For example:
 
 
For uncomplicated diarrhea (grade 1 or 2 without complicating signs or symptoms), loperamide given at a standard dose (e.g. initial administration of 4 mg, then 2 mg every 2-4 hours, maximum of 16 mg/day), along with oral hydration and dietetic measures should be considered. Note: complicating signs or symptoms include: moderate to severe cramping, decreased performance status, fever, neutropenia, frank bleeding or dehydration.
 
For complicated diarrhea (all grade 3 or 4, grade 1-2 with complicating signs or symptoms), management should involve intravenous (IV) fluids, and consider treatment with octreotide (at starting dose of 100 to 150 µg sub-cutaneous tid or 25 to 50 µg IV) and antibiotics (e.g. fluoroquinolone) should be given.
 

Nausea and Vomiting	
The investigator should consider/investigate potential concomitant medication, food or comorbidity driven causes of nausea and/or vomiting and remedy these causes if possible (e.g. discontinuation of concomitant medication, dietary modification, treatment of comorbidity).
 
Individualized supportive and anti-emetic treatment should be initiated, as appropriate, at the first signs and/or symptoms of these AEs. In patients with vomiting, the patient should be monitored for signs of dehydration and instructed to take preventive measures against dehydration.
 
Concomitant medication for the treatment of nausea and/or vomiting should follow local practice and the investigator's best judgment.

SKIN TOXICITY (rash and photosensitivity)  CTCAE grade 1  CTCAE grade 2  ≥ CTCAE grade 3	
Consider to initiate institute appropriate skin toxicity therapy (such as antihistamines, topical corticosteroids and low-dose systemic corticosteroids)
 
Initiate/intensify appropriate skin toxicity therapy (such as antihistamines, topical corticosteroids and low-dose systemic corticosteroids).
 
Intensify appropriate skin toxicity therapy and monitor weekly or more frequently until resolved to grade ≤ 2

TOXICITY	FOLLOW-UP EVALUATION
Peripheral edema ≤ CTCAE grade 2	Consider to initiate conservative measures such as leg elevation, compression stockings, and dietary salt modification as clinically indicated
≥ CTCAE grade 3	Initiate/intensify conservative measures
RESPIRATORY DISORDERS ILD /Pneumonitis	
CTCAE Grade 1	CT scan (high-resolution with lung windows) recommended, with serial imaging to monitor for resolution or progression - re-image at least every 3 weeks Monitor for symptoms every 2-3 days - Clinical evaluation and laboratory work-up for infection Monitoring of oxygenation via pulse oximetry recommended Consultation of pulmonologist recommended
CTCAE Grade 2	CT scan (high-resolution with lung windows) 
 
Monitor symptoms daily, consider hospitalization
 
Clinical evaluation and laboratory work up for infection
 
Consult pulmonologist
 
Pulmonary function tests a - if normal at baseline, repeat every 8 weeks
 
Bronchoscopy with biopsy and/or BAL recommended c
 
Symptomatic therapy including corticosteroids if clinically indicated (1 to 2 mg/kg/day prednisone or equivalent as clinically indicated) b
 

CTCAE Grade 3 and Grade 4	CT scan (high-resolution with lung windows) Clinical evaluation and laboratory work-up for infection Consult pulmonologist Pulmonary function tests a - if < normal, repeat every 8 weeks until ≥ normal Bronchoscopy with biopsy and/or BAL if possible c Treat with IV steroids (methylprednisolone 125 mg) as indicated. When symptoms improve to ≤ Grade 1, a high dose oral steroid (prednisone 1 to 2 mg/kg once per day or dexamethasone 4 mg every 4 hours) b . If IV steroids followed by high dose oral steroids does not reduce initial symptoms within 48 to 72 hours, consider non-corticosteroid immunosuppressive medication

\*Note: this table refers only to the evaluation schedule to monitor selected toxicities. Refer to [Table 6-3](#) for dose modifications required for applicable toxicities

\*\*Note: except if the patient is Grade 2 at baseline in which case: it is ≥ CTCAE grade 3

a PFT (Pulmonary function tests) to include: diffusing capacity corrected for hemoglobin (DLCO); spirometry; resting oxygen saturation

Guideline for significant deterioration in lung function: Decrease in spirometry and/or DLCO of 30% and/or O2 saturation ≤ 88% at rest on room air.

b Duration and dose of course of corticosteroids will vary according to circumstances but should be as limited as possible. Consider tapering dosage at end.

c If bronchoscopy is performed, bronchoalveolar lavage (BAL) should be done where possible to exclude alveolar hemorrhage, opportunistic infections, cell count + determination lymphocyte CD4/8 count where possible.

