A study to evaluate the effect of itraconazole (strong CYP3A4 inhibitor) and rifampicin (strong CYP3A4 inducer) on the single-dose pharmacokinetics of INC280 in healthy subjects was completed [CINC280A2102]. When co-administered with itraconazole, INC280 AUC increased by approximately 40%. There was no change in Cmax. When co-administered with rifampicin, INC280 AUC and Cmax decreased by approximately 66% and 56%, respectively. The result indicated that INC280 is not a sensitive CYP3A4 substrate. Given that the reduction in exposure by strong CYP3A4 inducers could potentially compromise the efficacy, the concurrent use of strong CYP3A4 inducers with INC280 should be avoided.

INC280 does not show a risk of QT prolongation. Preliminary analysis on 110 patients in study [CINC280A2201] showed that no patients had new post-baseline QTcF values greater than 500 ms. Changes from baseline ( $\Delta$ QTcF) greater than 60 ms were not observed and changes greater than 30 ms and below 60 ms were observed in 4 patients (4/110, 3.6%). The observed mean QTcF changes from baseline around Tmax (2 hours post-dose) were 5.21 ms on Cycle 1 Day 1 and -0.54 ms on Cycle 1 Day 15. Based on the PK/QT analysis, the estimated mean  $\Delta$ QTcF (upper one-sided 95% CI) at mean steady state INC280 concentration

2 hours post-dose (4584 ng/mL) was 0.11 ms (1.85 ms) at the recommended phase 2 dose of 400 mg BID with tablets. The upper one-sided 95% CIs for the estimated mean  $\Delta$ QTcF at clinically relevant INC280 concentrations are below the regulatory threshold of 10 ms. For more information, please refer to the current INC280 [Investigator's Brochure].

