## 6.4 Concomitant medications

Drugs in [Table 6-5](#) and [Table 6-6](#) are presented by mechanism of interaction. [Table 6-7](#) presents drugs known to cause Torsades des Pointes.

In general, the use of any concomitant medication/therapy deemed necessary for the care of the patient (e.g. such as anti-emetics, anti-diarrhea) is permitted (see [Section 6.4.1](#)), except when specifically prohibited (see [Section 6.4.3](#)).

The patient must be told to notify the investigational site about any new medications he/she takes after the start of the study drug. All medications (excluding study treatment and prior antineoplastic treatments), blood transfusions, surgeries and procedures (including physical therapy) administered within 28 days prior to the first dose administration of INC280 through 30 days after the last dose of INC280 will be recorded in the Concomitant Medications or Surgical and Medical Procedures eCRF, respectively. Medications include not only physician prescribed medications, but also all over-the counter medications, herbal medications, food supplements and vitamins.

The following restrictions apply during the entire duration of the study:

- No other investigational therapy should be given to patients
- No anticancer agents other than the study medication (INC280) should be given to patients.

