### 6.4.1 Permitted concomitant therapy

Patients are permitted to use the following medications while taking INC280:

- Oral or topical antibiotics
- Medications to prevent or treat nausea, vomiting or diarrhea
- Growth factors (e.g. G-CSF, GM-CSF, erythropoietin, platelets growth factors, etc.) are allowed per the investigator's judgement and per local guidelines.
- Treatment with bisphosphonates for pre-existing bone metastases is permitted, if clinically indicated, and following existing local guidelines. Treatment with bisphosphonates should preferably begin before the study treatment is initiated, but can also be initiated during therapy only if absence of radiological bone disease progression is well documented (in this case, the reason for its use must be clearly documented; i.e. "pre-existing, non-progressing, bone metastases").
- Oxygen therapy and blood products or transfusions
- Nutritional support or appetite stimulants
- Pain medication
- Local bone radiotherapy for analgesic purposes or for lytic lesions at risk of fracture may be carried out if required. If palliative radiotherapy is initiated after start of study treatment, the reason for its use must be clearly documented and progression as per RECIST 1.1 must be ruled out. The study treatment must be interrupted on the days of radiotherapy and can be resumed the day after its completion.

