#### 6.4.3 Prohibited concomitant therapy

- Co-administrating INC280 with strong CYP3A4 inducer (rifampicin) decreased INC280 AUC by 66% and Cmax by 56%. Concurrent use of strong CYP3A4 inducers is prohibited as decreased INC280 exposure may lead to reduced efficacy.
- Drugs with a known risk of Torsades des Pointes (TdP) are prohibited. For identification of drugs with known risk of TdP please refer to [qtdrugs.org](http://qtdrugs.org) (refer to [Table 6-7](#)).

Patients enrolled in this study are not permitted to participate in additional parallel investigational drug or device studies while on treatment.

The prohibited medications are listed in the [Table 6-6](#) and [Table 6-7](#) below.

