**Table 6-6 Drugs prohibited while on study**

Mechanism of Interaction	Drug Name
Strong CYP3A4 inducer	carbamazepine, enzalutamide, lumacaftor, phenobarbital, phenytoin, rifabutin, rifampicin, mitotane, St. John's wort ( Hypericum perforatum )

Source: The list is adapted from the Novartis Institutes for Biomedical PK Sciences internal memorandum (Jan 2018): drug-drug interactions (DDI) database, which is compiled primarily from the Indiana University School of Medicine's "Clinically Relevant" Table (medicine.iupui.edu/flockhart/table.htm), the University of Washington's Drug Interaction Database (druginteractioninfo.org), and the FDA's "Guidance for Industry, Drug Interaction Studies" This may not be an exhaustive list, will be updated periodically.

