**Table 6-7 Drugs with a known risk of Torsades des Pointes prohibited while on study**

Class of medication	Drug Name
With Known risk of Torsades des Pointes	amiodarone, anagrelide, arsenic trioxide, astemizole, azithromycin, chloroquine, chlorpromazine, cilostazol, ciprofloxacin, cisapride, citalopram, clarithromycin, disopyramide, dofetilide, domperidone, donepezil, dronedarone,

Class of medication	Drug Name
	droperidol, erythromycin, escitalopram, flecainide, fluconazole, gatifloxacin, halofantrine, haloperidol, ibutilide, levofloxacin, levomepromazine, levosulpiride, methadone, moxifloxacin, ondansetron, oxaliplatin, papaverine HCl (intra-coronary), pentamidine, pimozide, procainamide, propofol, quinidine, roxithromycin, sevoflurane, sotalol, sulpiride, sultopride, terlipressin, terodilene, thioridazine, vandetanib
This may not be an exhaustive list. Check: crediblemeds.org/healthcare-providers/drug-list for the most updated list.	

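### At QTcF ≥ 501 ms, Table 6-4 sends sites to Table 6-6 for QT-prolonging drugs, but that list is Table 6-7

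*Protocol*

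**What the plan says.** Protocol Table 6-4 sets out follow-up for selected toxicities. Its cardiac row lists the actions to take at a QTcF of 501 ms or more. One of them is a review of co-medication in two parts: potential to inhibit CYP3A4/5, with Table 6-5 cited, "and/or to prolong the QT-interval", with Table 6-6 cited.

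The tables and the sections that introduce them read as follows:

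- "Table 6-6 Drugs prohibited while on study" has a single mechanism row, strong CYP3A4 inducers.
- "Table 6-7 Drugs with a known risk of Torsades des Pointes prohibited while on study" is the QT-related list. Its footnote says that it may be incomplete and links to an online list.
- Section 6.4 describes Tables 6-5 and 6-6 as organised by interaction mechanism and says that Table 6-7 "presents drugs known to cause Torsades des Pointes".
- Section 6.4.3 states: "Drugs with a known risk of Torsades des Pointes (TdP) are prohibited". It refers the reader to Table 6-7.

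**The concern.** The bullet is used when a grade 3 QTc prolongation has just been recorded. A site that follows the printed table number arrives at a list of enzyme inducers with no QT or Torsades category, and could conclude that no relevant co-medication is present.

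Table 6-7 drugs are prohibited, so none should be in use, but use by oversight is plausible. Section 6.4.1 permits oral antibiotics and "Medications to prevent or treat nausea, vomiting or diarrhea". For complicated diarrhea, another row of Table 6-4 says that "antibiotics (e.g. fluoroquinolone) should be given". Table 6-7 prohibits four fluoroquinolones and also ondansetron. Such supportive drugs will often be wanted: Section 1.2.1.2.1 reports drug-related nausea in 32.8% of patients in this study, vomiting in 19.2% and diarrhea in 11.6%.

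Finding such a drug has consequences. Section 7.1.4 requires study treatment to stop when a prohibited treatment has been used, whereas Table 6-3 lets INC280 resume at the same dose if a grade 3 QTc prolongation resolves within 7 days. Neither rule is wrong, but which one is applied can depend on whether the drug is found.

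**Working it through.** **Cross-references.** The claim is about a pointer, so the first step is to compare each citation in the bullet with the table it names.

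| Part of the bullet | Table cited | What that table holds | Correct? |
|---|---|---|---|
| CYP3A4/5 inhibition | 6-5 | Includes a strong CYP3A inhibitor row | Yes |
| QT prolongation | 6-6 | Strong CYP3A4 inducers only | No; should be 6-7 |

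Sections 6.4 and 6.4.3 agree with each other that Table 6-7 is the Torsades list. Only the bullet in Table 6-4 differs. It is part of the current protocol body, not of an amendment summary, and the table number is printed in full.

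**Could the cited tables serve as a substitute?** Counting and comparing entries:

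- Table 6-6: 9 agents.
- Table 6-7: 48 drugs.
- In both 6-6 and 6-7: 0.
- In both 6-5 and 6-7: 0.
- Fluoroquinolones in 6-7: 4 (ciprofloxacin, gatifloxacin, levofloxacin, moxifloxacin).

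A site that opens both cited tables therefore sees none of the 48 drugs. This fits the Amendment 6 change under which each drug is listed once, in the most restrictive table that applies.

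**How often would the bullet be used?** Section 1.2.1.2.4 reports a preliminary analysis of 110 patients in this study that "showed that no patients had new post-baseline QTcF values greater than 500 ms", so the observed count is 0 of 110. With zero events in n patients, the exact one-sided 95% upper limit is

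1 − 0.05^(1/n) = 1 − 0.05^(1/110) = 0.0269, or 2.7%.

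The SAP (Section 2.2, combined cohorts) gives 373 patients in all. Applying the limit to that total: 0.0269 × 373 = 10.0. The plausible number of patients who reach the bullet is thus 0 to about 10.

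**The case against.** The error itself is not in dispute; the argument is about its weight.

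- **The wording is clear and the right list is next to the wrong one.** The bullet says in words what to look for. The protocol's list of tables puts Tables 6-6 and 6-7 on the same page, and Section 6.4.3 introduces them together. This stands: a site that turns to Table 6-6 will probably see Table 6-7, whose title names Torsades.
- **Other safeguards do not rely on the pointer.** The drugs are already prohibited, concomitant medication is collected at every visit, and the same row requires a central manual read, an electrolyte check and a repeat ECG within one hour. Table 6-3 requires the dose to be omitted for grade 3 prolongation seen on at least two ECGs. This also stands, and it is why the risk is small.
- **The fluoroquinolone suggestion is a separate inconsistency.** Correcting the pointer leaves it in place, and Section 6.4 makes every permission subject to the prohibitions in Section 6.4.3. This is fair. The suggestion matters here only as one route by which a prohibited drug could be in use by mistake.
- **The figure of 10 does not measure harm.** It counts patients who reach the bullet. Harm would also need a Torsades drug in use and a site that stopped at the wrong list, and the documents give no rate for either. This is correct, so the figure should be read only as a ceiling on use of the bullet.
- **There may be no one left to notify.** The SAP describes an analysis at last patient last visit, and the documents do not say how many patients remain on treatment. This limits the value of a site notice but does not make the table number right.

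**Conclusion.** The cross-reference is wrong as written. For QT-prolonging co-medication, Table 6-4 cites a list of 9 strong CYP3A4 inducers, while all 48 Torsades-risk drugs sit in Table 6-7 and none is in either cited table. It is a wrong pointer in operative safety text, not a missing check. The ORR and DOR analyses, sample size, error rates, and dose and stopping rules are unaffected.

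The practical risk is small: 0 of 110 patients had a new QTcF above 500 ms, and the upper limit corresponds to about 10 of 373 patients. That projection assumes that the preliminary rate, with the follow-up those 110 patients had, applies to the whole study. It says nothing about how many sites would be misled. The correction is still worth making, because it applies to a serious cardiac finding and costs almost nothing.

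**What to change.** In the QTcF ≥ 501 ms entry of Table 6-4, replace the Table 6-6 citation for QT prolongation with Table 6-7 and the online list linked in its footnote. Leave the Table 6-5 citation as it is. Send a short notice to any site that still has patients on treatment; if none remain, no notice is needed.

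The cost is one table number and, where relevant, a brief communication. It adds no procedure and changes no dose or stopping rule.
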